Sample Size and Power: The goal of this pilot study is to estimate the cessation rates in each arm to obtain an effect size for future larger studies. To conduct a hypothesis test for the comparison of cessation rates between the two intervention arms will require a minimum 199 people in each arm (total sample=398) for at least 80% power. This calculation was based on a 2-sided test with the type I error of 0.05, and assuming a 20% cessation rate in the *Sense2Quit App* group (intervention) and a 10% cessation rate in the control arm. The 10% difference would be equivalent to a medium effect size (Cohen's $d=0.45$). In this pilot study, we propose a total sample of 60 (30 per group) of whom we expect there to be 20% attrition. Therefore, this study is not powered to detect a significant difference between study arms. Instead, for the sample size (30 per group), this study will have at least 80% probability that the standard error of the cessation rate estimates $\leq 7\%$. We assume that the expected cessation rates range from 10% to 20%, and therefore the sample size is sufficient to provide a power estimation for a larger trial with acceptable reliability.

Recruitment and Retention: Strategies for recruitment and retention are described in the Recruitment and Retention attachment. We will enroll 60 PLWH who smoke tobacco. Inclusion/exclusion criteria are described above.

Screening: Potential study participants will provide verbal informed consent by phone or complete an eConsent form through REDCap prior to completing a phone screening process that assesses eligibility. If eligible, participants will attend a baseline session described below.

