Paradata Data Analysis: At the individual level, we will understand participants' use of the App over time through the collection of paradata⁸⁹ which is "free" in that it does not require any additional effort from the user⁹⁰. To explore barriers and facilitators to widespread implementation of *Sense2Quit App*, we will collect data during intervention, implementation, and after the trial has ended. The primary paradata to be collected are page accessed, time stamp, and device type. From these data, we will derive the following use of data for each session: duration on each page, page progression through the application, time from login to result, and total time from login to logout. We will analyze the data at the individual-level (i.e., user-level), application-level, page-level, and session-level and assess how these differ by demographic characteristics, technology use, and outcome measures. Additionally, we will measure the amount in bytes of user data transmitted. Importantly, longitudinal analysis will determine if the user experience changes with repeated use. The paradata collected from each page will be analyzed to generate a "heatmap" of user-interaction (i.e., the distribution of activity for each link/button) that will inform user duration on each page of the App and user interaction with App content, contact pages, and the help page. We will explore usability issues with consideration for how many times users accessed help and what page of the App referred them to the help, implying the need for clarification. We will analyze differences in aggregated data by demographic group (e.g., age) to better understand engagement with the intervention and potential facilitators and barriers to App use.

Plan for Future Fully Powered RCT of *Sense2Quit*. At the end of Year 2, we will write an R01, which will include a full- scale trial of the final *Sense2Quit App* with the same sample. Importantly, process evaluation interviews will allow us to refine the intervention in preparation for the RCT. We will also assess the intervention's sustainability, and with key stakeholders, develop specific strategies to scale up the intervention to reach more PLWH who smoke within additional community-based and clinical settings.

AIM 4: Testing with Confounding Gestures

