Possible AEs that are unanticipated will be brought to the attention of the Coordinators and reported immediately to both site IRBs. All study staff will be trained to recognize and report AEs and SAEs. Possible AEs will immediately (within 24 hours) be brought to the attention of the Lead at each site by study staff who identify the event. The Site Lead will report the AEs and SAEs to the IRB in writing as soon as possible, but within 7 calendar days for death or life-threatening events and within 15 calendar days for all other AEs or SAEs. The IRBs will determine whether it is appropriate to stop the study protocol temporarily or will provide suggestions/modifications to the study procedures as necessary. Possible modifications include adding these possible adverse events to the consent form and re-consenting all study participants. The PIs will be responsible for monitoring participant safety on a monthly basis at regularly scheduled research meetings. They will keep a written log of all events and ensure that the IRB is contacted immediately. They will also keep a log of the outcome of IRB decisions regarding AEs and apprise the research team of any changes that need to occur because of IRB decisions.

STATISTICAL DESIGN AND POWER

Sample Size and Power. The goal of this pilot study is to estimate the smoking cessation rates in each arm to obtain an effect size for future larger studies. To conduct a hypothesis test for the comparison of cessation rates between the two intervention arms, it requires a minimal sample size of 199 per group (total 398) for at least 80% power. This calculation was based on a 2-sided test with the type I error of 0.05, and assuming a 20% cessation rate in the *Sense2Quit* App group (intervention) and a 10% cessation rate in the control arm. The 10% difference would be equivalent to a medium effect size (Cohen's $d=0.45$). In this pilot study, we propose a total sample of 60 (30 per group). Therefore, this study is not powered to detect a significant difference between arms. Instead, we estimated the minimal sample size for the estimation of cessation rates in each arm with acceptable reliability. For the sample size (30 per group), this study will have at least 80% probability that the standard error of the cessation rate estimates $\leq 7\%$, assuming expected cessation rates ranging from 10% to 20%. Therefore, the sample size is sufficient to provide estimation with acceptable reliability.

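### Thirty per arm does not give a reliable power estimate for the larger trial: the stated precision concerns each arm's rate, not the difference between arms

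*Combined protocol and SAP*

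**What the plan says.** AIM 2, Sample Size and Power, gives the pilot's goal as "to estimate the cessation rates in each arm to obtain an effect size for future larger studies". It reports that a test comparing the arms "will require a minimum 199 people in each arm (total sample=398) for at least 80% power", with the intervention rate set at 20% and "a 10% cessation rate in the control arm", and it accepts that 60 participants cannot support that test. It then offers a precision argument: with 30 per arm there is at least an 80% chance that the standard error of a cessation rate is 7% or less, for rates between 10% and 20%. From this it concludes that "the sample size is sufficient to provide a power estimation for a larger trial with acceptable reliability".

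STATISTICAL DESIGN AND POWER, Sample Size and Power, repeats the effect-size goal and the precision argument but ends more modestly: "Therefore, the sample size is sufficient to provide estimation with acceptable reliability".

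The use to be made of the results appears under AIM 3, Plan for Future Fully Powered RCT: "At the end of Year 2, we will write an R01". No section says how that trial's size will be derived from the pilot.

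**The concern.** The precision statement concerns one arm at a time. The size of a two-arm trial is driven by the inverse square of the difference between arms, and neither sample-size section gives any precision for that difference. A reader of AIM 2 would take the pilot's observed effect to be a sound basis for sizing the next trial. With 30 per arm it is not. If the later application relied on it, a pilot that happened to show a large difference would produce an underpowered trial, and one that showed a small difference would produce an impractically large one. The sentence also matters because it is the plan's stated justification for the pilot's size.

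**Working it through.** **Inputs.** From AIM 2, Sample Size and Power: two-sided type I error 0.05, power 80%, rates 20% and 10%, 30 per arm. From AIM 2, Procedures: 1:1 allocation. From AIM 2, Data Analysis: participants lost to follow-up count as smokers, so the denominator stays at 30. I take 20% and 10% as true rates on that denominator.

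**1. The plan's own figure.** Pooled two-proportion formula, no continuity correction:

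n = [1.960·√(2·p̄(1−p̄)) + 0.8416·√(p₁(1−p₁) + p₂(1−p₂))]² / (p₁−p₂)²

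With p₁ = 0.20, p₂ = 0.10 and p̄ = 0.15: (0.9897 + 0.4208)² / 0.01 = 198.96, so 199 per arm. The plan's figure reproduces.

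**2. Precision of the difference.**
- Single arms: √(0.10·0.90/30) = 5.5 points and √(0.20·0.80/30) = 7.3 points.
- Difference: √(0.09/30 + 0.16/30) = √(0.25/30) = 9.1 points.
- 95% half-width: 1.96 × 9.1 = 17.9 points, against an effect of 10 points.

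Whether the per-arm criterion of 7% is itself met is a separate question and is not needed here.

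**3. What this does to a computed trial size.** As an assumption, put each possible pair of quitter counts into the formula of step 1, weighting by Binomial(30, 0.20) and Binomial(30, 0.10). Ties occur with probability 8.1% and reversals with 9.8%, together 17.9%; these give no usable size.

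| Convention | 25th percentile | Median | 75th percentile |
|---|---|---|---|
| All pilots, ties and reversals as no finite size | 74 | 199 | 1,455 |
| Only pilots favouring the app (82.1%) | 62 | 122 | 407 |
| Sign of the difference ignored, ties as no finite size | 71 | 172 | 631 |

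Over all pilots:
- 48.7% give a size below 199.
- 31.8% give 99 or fewer. True power at 20% versus 10% is about 50% with 99 per arm and 40% with 74.
- 12.9% give a size between 150 and 250.
- 29.6% give a size within a factor of two of 199.

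The formula variant hardly matters. On the first convention, the middle half is 71 to 1,453 with an unpooled variance and 68 to 1,450 with the arcsine method. With 24 per arm (20% attrition, completers only) it is 63 to 1,377.

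**4. Sensitivity to single quitters.** Six versus three quitters gives 199. Changing one quitter gives 122 (7 v 3), 101 (6 v 2), 407 (5 v 3) or 490 (6 v 4), a change of about 1.6- to 2.5-fold.

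**5. Sizing on a fixed difference.** Suppose 3 of 30 control participants quit. The Clopper-Pearson interval is 2.1% to 26.5%. For a fixed 10-point difference, the formula of step 1 gives 103 per arm at a control rate of 2.1%, 199 at 10% and 338 at 26.5%. That is still wide, but it is bounded and does not depend on the observed difference.

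**The case against.** The strongest defence is that this is a pilot and the plan says so. Both sample-size sections state that it is not powered for a comparison, the analysis is descriptive with exact intervals for each arm, and feasibility and acceptability are aims alongside preliminary efficacy. Nothing in the trial's conduct depends on the sentence, and any harm falls on a later application that is not before us. This stands, and it limits the severity. It does not rescue the inference: conceding low power for a test does not make the same noisy difference a reliable basis for a power calculation.

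Four stronger readings are tempting but not supported.
- **A plug-in rule.** A reader might infer that the observed difference alone will set the next trial's size. The plan speaks only of an effect size and a power estimation, so step 3 is a consequence under an assumption.
- **Programme stopping.** A reader might infer that a chance zero difference would end the programme. No such rule appears.
- **The second section.** A reader might take the closing sentence under STATISTICAL DESIGN AND POWER as the same claim. It concerns estimating each arm's rate; only the effect-size goal stated there overlaps.
- **The 20-fold range.** The upper figure of 1,455 depends on counting ties and reversals as no usable size. Among favourable pilots the range is 62 to 407, about 6.5-fold. That is still far too wide to call reliable.

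**Conclusion.** The conclusion drawn in AIM 2 does not follow from the criterion offered for it. The difference between arms has a standard error of 9.1 points against a 10-point effect, and no reasonable convention makes a trial size computed from it stable: the narrowest middle-half range at 30 per arm is 62 to 407. The trial-size figures rest on three assumptions: true rates of 20% and 10%, 30 per arm with losses counted as smokers, and direct use of the observed rates in the plan's formula. The standard error of the difference needs only the first two.

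This should be fixed, but it does not threaten the pilot's conduct. It is an unsupported inference. A reader might call it an arithmetic error, but the plan's 199 per arm is correct.

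**What to change.** **AIM 2, Sample Size and Power.** Delete the statement that the sample gives a power estimation with acceptable reliability. Say instead that:
- the pilot difference will be reported with its confidence interval but will not by itself set the size of the larger trial;
- that trial will be sized on a prespecified worthwhile difference. The 10 points behind the 199 per arm could serve, but the sponsor would need to justify it, since the documents do not present it as the smallest worthwhile effect;
- the pilot will supply the control-arm rate and retention, with the required size shown across the control rate's 95% interval, as in step 5 of the working.

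**STATISTICAL DESIGN AND POWER, Sample Size and Power.** Align only the effect-size goal with the new text. The closing sentence need not change on this ground.

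**Cost.** A few sentences, with no new data or participants. The pilot's stated justification becomes slightly less favourable.

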Procedures: Eligible participants will attend a baseline visit at Columbia University School of Nursing. On the day of their baseline appointment, study participants will meet a study staff member who is trained by a nurse. The study staff member will run the baseline appointment. Upon arrival, participants will be asked to blow into a breath analyzer to complete assessment of their study eligibility. Breath samples will be analyzed for exhaled carbon monoxide (CO) levels (in ppm) using a breathalyzer (MicroTM basic Smokerlyzer[®]). After providing written consent, participants will complete a baseline questionnaire (See **Table 3**). They will be asked complete a timeline to follow back to track their cigarette use for the previous 30 days and to complete the Fagerstrom Test for Nicotine Dependence. Survey instruments will be collected through Qualtrics at baseline, and 4 weeks, and 12 weeks after baseline.

Following completion of baseline study instruments, participants will be randomized (1:1) to the App arm or the control arm, stratified by sex assigned at birth. Participants in both arms will undergo a smoking cessation counseling session. Notes from the counseling session will be recorded on RedCap. Participants will receive an informational packet during the counseling session which will consist of: 1) an appointment reminder sheet, nicotine patch information, nicotine gum information, nicotine lozenge information and smoking substitution ideas (Intervention) or 2) a reminder sheet, NYS Quitline information, and smoking substitution ideas (control). Participants in the control arm will be referred to the New York State Smoker's Quitline. Through the Quitline, participants in the control arm can receive NRT if desired and receive additional smoking cessation counseling. A study staff member will follow up to see how many participants called, texted and/or visited the Quitline webpage. Participants in the intervention arm (App arm) will be provided with combination NRT. Participants will be given an 8-week supply of combination NRT and will be instructed to begin using their NRT supply directly after their baseline visit.

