Marker of HIV/AIDS immune status	CD4, viral load (chart review), Case Adherence Index (self-report) ⁸⁶
Follow Up Visit Only	
Pharmacotherapy Use	Nicotine replacement therapy Adherence
Intervention Quality	Health-ITUES ⁶³ ; Post-System Study Usability (PSSUQ) ⁸⁷ , Intervention ratings

Operationalization of Outcome Measures:

The primary outcome for determining preliminary efficacy will be biochemically (saliva cotinine) validated 7-day point prevalence abstinence.

Subjective Data (e.g., health status, quality of life) and system use will be obtained from subjects for the specific research purposes of this study. Follow-up visits will be completed on-site at the study location.

Carbon Monoxide Monitoring. We will be using a carbon monoxide detector to biochemically verify tobacco use. *Medical Records.* We will be reviewing patient records to assess participants' CD4 and viral loads. For participants who are not patients at CUIMC, they will be asked to bring in their most recent CD4/viral load laboratory data from their last visit to their healthcare provider.

Compensation: Eligible participants will be able to receive \$40 for completing baseline study procedures, \$50 at the 4-week follow-up study visit, and \$60 at the 12-week follow-up study visit.

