Data Analysis: This is a pilot study to assess preliminary feasibility, acceptability, and efficacy. Descriptive statistics will be used for all analyses. The rate of quit attempts will be calculated as the proportion of smokers who attempt to quit (i.e., no smoking during a 24 hours period); 7-day point prevalence abstinence will be calculated as the proportion of smokers who are biochemically verified (saliva cotinine) 7-day abstinence at a given time point; and sustained abstinence will be calculated as proportion of days of no smoking starting on the quit date among those who attempt to quit. We will provide point estimates and corresponding confidence intervals of these measures for each arm. Because of our small sample sizes, we will obtain Clopper-Pearson exact confidence intervals based on the binomial distribution. Given the small sample size, the purpose of the arms is to monitor for unexpected, gross differences between the two groups. To determine acceptability, we will ask participants in both arms how useful each of the intervention components were (1 = *Not at all useful* to 7 = *Extremely useful*) and whether they would recommend the program to a friend (1 = *Definitely would not recommend* to 7 = *Definitely would recommend*). For the intervention to be deemed acceptable, the mean level for each of these measures would have to be five or

higher. The efficacy of the intervention will be based on saliva- confirmed 7-day point prevalence abstinence at the final study visit. Lost-to-follow-up participants will be included as smokers.

NOT-OD-15-102: Consideration of Sex as a Biological Variable: In accordance with NIH guidance, we will include sex as a biological variable in the study design (enroll equal numbers of males and females), analyses, and reporting. We will report all primary and secondary outcomes separately by sex to enhance rigor and transparency of our findings in addition to including sex in all multivariate models.

AIM 3: Employ the RE-AIM framework to assess the potential scale-up of the *Sense2Quit App*.

In addition to testing the Efficacy of the *Sense2Quit App*, we will concurrently measure the four remaining RE-AIM dimensions⁸⁸ as follows:

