Statistical Design and Data Analysis: This is a pilot study to assess preliminary feasibility, acceptability, and preliminary efficacy. Descriptive statistics will be used for all analyses. The rate of quit attempts will be calculated as the proportion of smokers who attempt to quit (i.e., no smoking during a 24-hour period); 7-day point prevalence abstinence will be calculated as the proportion of smokers who are biochemically verified 7-day abstinence at a given time point; and sustained abstinence will be calculated as proportion of days of no smoking starting on the quit date among those who attempt to quit. We will provide point estimates and corresponding confidence intervals of these measures for each arm. Because of small sample sizes, we will obtain Clopper-Pearson exact confidence intervals based on the binomial distribution. Given the small sample size, the purpose of the arms is simply to monitor for unexpected, gross differences between the two groups. To determine acceptability, we will ask participants in both arms how useful each of the intervention components were (1 = *Not at all useful* to 7 = *Extremely useful*) and whether they would recommend the program to a friend (1 = *Definitely would not recommend* to 7 = *Definitely would recommend*). For the intervention to be deemed acceptable, the mean level for each of these measures would have to be 5 or higher. The efficacy of the intervention will be based on saliva-confirmed 7-day point prevalence abstinence at the follow-up survey. Lost-to-follow-up participants will be included as smokers.

DISSEMINATION PLAN

Tools developed and evaluated during this project have the potential to extend the impact and reach of tobacco cessation for all smokers but specifically for persons living with HIV (PLWH) who smoke. Per the RFA, this study was designed for dissemination (e.g., feasibility/acceptability of the intervention for PLWH) and suitable for the intended context.

Therefore, a multi-faceted dissemination plan targeting various stakeholders is proposed. We will disseminate our findings to technology-oriented and clinical management-oriented audiences. For technology audiences, we will provide enough detail to enable the *Sense2Quit App* to be constructed and used within an appropriate context.

We propose the following dissemination strategies:

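### Abstinence is verified by saliva cotinine with no rule for NRT users and with CO as an unreconciled second verifier: week-4 rates can be biased against the app, the week-12 primary rate only through people still using NRT

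*Combined protocol and SAP*

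**What the plan says.** The outcome definition in Aim 2, Operationalization of Outcome Measures, reads: "The primary outcome for determining preliminary efficacy will be biochemically (saliva cotinine) validated 7-day point prevalence abstinence". Aim 2, Data Analysis, counts smokers "who are biochemically verified (saliva cotinine) 7-day abstinence at a given time point", so the marker applies at week 4 as well as week 12. That section bases efficacy on saliva, "confirmed 7-day point prevalence abstinence at the final study visit". The later Statistical Design and Data Analysis section has "saliva-confirmed 7-day point prevalence abstinence at the follow-up survey" and does not say which of the two follow-up visits is meant. Table 3 also ties 7-day abstinence to saliva cotinine.

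Exhaled CO appears as well. Table 3 lists it beside cotinine. The Carbon Monoxide Monitoring paragraph gives it the task of biochemically verifying tobacco use. The account of the week-4 and week-12 visits in Aim 2, Procedures, mentions a breath sample but no saliva sample.

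On NRT, Aim 2, Procedures, says of the active arm: "Participants will be given an 8-week supply of combination NRT", to be started directly after baseline. The app also prompts its use. For controls: "Through the Quitline, participants in the control arm can receive NRT if desired", with no amount or duration given. The Overview tells participants that gum or lozenge can be bought over the counter. Table 3 lists an NRT adherence item at follow-up visits, and Limitations and Alternatives says that NRT use is self-reported. None of these places links NRT use to the abstinence definition.

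**The concern.** Cotinine is formed from nicotine whatever its source, so it cannot by itself separate a cigarette from a patch, gum or lozenge. That is the one premise here from outside the documents. The trial gives NRT directly to one arm and leaves it optional in the other. A participant who follows the assigned treatment and stops smoking may therefore fail verification, and this may happen more often in the active arm.

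The estimates themselves are at stake. Sample Size and Power says: "The goal of this pilot study is to estimate the cessation rates in each arm to obtain an effect size for future larger studies". A verified rate that mixes smoking with NRT use passes that mixture on to the next trial's planning. With two verifiers named and no order of precedence, the classification of a participant with positive cotinine and low CO could also be settled after results are seen.

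**Working it through.** **Reproducing the plan's figure.** Inputs from Sample Size and Power: 20% versus 10%, two-sided 0.05, 80% power. With pooled variance under the null and no continuity correction, n = [1.960·√(2·0.15·0.85) + 0.842·√(0.20·0.80 + 0.10·0.90)]² / 0.10² = 199 per arm, as stated.

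**Timing.** The supply runs nominally from week 0 to week 8. Week 4 lies inside it; week 12 lies 12 − 8 = 4 weeks after it.

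**Model.** Let a and c be the shares of true abstainers using NRT at the visit in the active and control arms, and s the share of those users who fail cotinine verification, taken as equal in both arms. The documents give none of these, so every value is an assumption.

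- Verified rate, active: 0.20(1 − s·a)
- Verified rate, control: 0.10(1 − s·c)
- Difference: 0.10 − s(0.20a − 0.10c)

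For any s above zero, the difference falls below the true 0.10 exactly when c < 2a. The size of the shrinkage depends on s.

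**Week 4, true difference +10 points**

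| a / c | All fail (s = 1) | Half fail (s = 0.5) |
|---|---|---|
| 50% / 20% | 10% vs 8%, +2 | 15% vs 9%, +6 |
| 80% / 20% | 4% vs 8%, −4 | 12% vs 9%, +3 |
| 80% / 80% | 4% vs 2%, +2 | 12% vs 6%, +6 |
| 30% / 60% | 14% vs 4%, +10 | 17% vs 7%, +10 |
| 30% / 70% | 14% vs 3%, +11 | 17% vs 6.5%, +10.5 |

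Equal NRT use still shrinks the difference, because the same proportional loss is taken from a larger rate. At s = 0.5 the sign cannot reverse: even a = 1, c = 0 gives 10% vs 10%.

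**Week 12, all fail, with the next trial sized by the same formula**

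| a / c | Verified rates | Difference | Per arm |
|---|---|---|---|
| 0% / 0% | 20% vs 10% | +10 | 199 |
| 20% / 5% | 16% vs 9.5% | +6.5 | 413 |
| 10% / 10% | 18% vs 9% | +9 | 226 |
| 10% / 20% | 18% vs 8% | +10 | 177 |
| 0% / 20% | 20% vs 8% | +12 | 131 |

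**Scale in this pilot.** Twenty percent of 30 is 6 expected active-arm quitters. Residual NRT use in 20% of them moves 6 × 0.20 = 1.2 people. The exact 95% intervals are 7.7–38.6% for 6/30 and 5.6–34.7% for 5/30.

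**The case against.** Four points can be made for the plan.

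First, CO is not a bystander: the protocol gives it a verification role. This stands, and it sets the form of the defect: two verifiers and no rule for disagreement, rather than no means of handling NRT users.

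Second, a reader might infer that the primary result is biased against the app. The documents do not support that. Efficacy is judged at the final visit, nominally four weeks after the supply ends, and the week-12 cases fall on both sides of the true difference. Continued use is possible in either arm, since over-the-counter products are mentioned and Quitline NRT has no stated end, but nothing shows how much or in which arm.

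Third, cases in which every NRT user fails are an upper bound, and the sign reversal at week 4 depends on them. This stands. Higher NRT use in the active arm is plausible from the design but is not quantified, and Limitations and Alternatives says that access in both arms is intended.

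Fourth, this is a descriptive pilot in which "the purpose of the arms is to monitor for unexpected, gross differences between the two groups". No test is harmed, and a shift of about one quitter lies well inside sampling error. But the rates and the effect size are what the pilot is meant to deliver, and larger samples do not remove misclassification.

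A reader might also infer that CO should simply replace cotinine as the primary marker. That is a debatable trade, not a necessity. For Aim 4 the protocol itself expects to recruit people who smoke yet fall below the CO entry level. If 5% of smokers reported abstinence and passed CO equally in both arms (assumed), the rates would be 0.20 + 0.80 × 0.05 = 24.0% and 0.10 + 0.90 × 0.05 = 14.5%, or 270 per arm; at 10%, 28.0% and 19.0%, or 348 per arm. Both exceed the 226 per arm under 10% residual NRT use in each arm.

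**Conclusion.** The concern holds in limited form. Saliva cotinine is the stated verifier at every time point, with no cut-off and no rule for NRT users, and the protocol does not settle how CO relates to it. At week 4 this can bias the verified difference against the app: it shrinks whenever the NRT-using share of control abstainers is below twice that of active abstainers. At an assumed 50%/20%, +10 points becomes +2 if all such users fail verification and +6 if half do. At week 12 the effect is confined to continuing NRT users, and its size and direction are unknown.

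These results rest on the plan's 20% and 10%, on cotinine responding to NRT, on equal failure shares in the two arms, and on NRT shares that the documents do not give. The missing rule is certain; material harm to the primary rate is not shown. It should be fixed because the remedy is cheap and the rates feed a larger trial.

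**What to change.** Pre-specify one classification rule, identical in both arms:

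- Participants reporting no NRT use in cotinine's detection window: self-reported 7-day abstinence verified by saliva cotinine, with the cut-off and window stated.
- Participants in either arm reporting NRT use in that window: verified by exhaled CO, with one pre-set cut-off strictly below the entry level of 5 in the inclusion criteria, so that no reading can both admit a smoker and verify abstinence.
- Sensitivity analysis: the CO-verified rate for all participants at weeks 4 and 12.
- Make the NRT item ask both arms about NRT from any source over that window before each visit, and tabulate it by arm.
- Reconcile Table 3, the visit narrative, Operationalization of Outcome Measures and both analysis sections on the marker, on saliva collection, and on week 12 as the primary visit.

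The cost is an amended outcome definition and at most one survey question. Breath samples are already planned at both follow-up visits, and the primary marker is kept.

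The rule relies on self-reported NRT use. CO has a shorter detection window and will pass some light smokers. If more active participants report NRT, more of that arm is judged by CO, and false passes may then favor the app. For example, with 5% false passes among smokers reporting NRT, NRT reported by 50% of active and 20% of control smokers, and no false passes by cotinine (all assumed), the rates are 0.20 + 0.80 × 0.50 × 0.05 = 22.0% and 0.10 + 0.90 × 0.20 × 0.05 = 10.9%, a difference of +11.1 points. The CO-for-all analysis is there to expose this.
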